### 5.4. Examination of Covariates, Other Strata and Subgroups

#### 5.4.1. Covariates and Other Strata

The list of covariates will be used in statistical analyses. Additional covariates and other strata of clinical interest may also be considered.

Category	Details
Strata	Not applicable
Covariates	
For primary efficacy analyses:
 
 
• Mixed model for repeated measurements (MMRM) including covariates of treatment group, baseline Hgb, visit, treatment-by-visit interaction, and baseline Hgb-by-visit interaction will be used.
 
 
For principal secondary efficacy analyses:
 
 
• Logistic regression model including treatment group and baseline Hgb as covariates will be used.
 

#### 5.4.2. Examination of Subgroups

The list of subgroups may be used in descriptive summaries and statistical analyses. Additional subgroups of clinical interest may also be considered.

Subgroup	Categories
Age (year)	< 65, >=65
Sex	Female, Male
Prior ESA dose (IU/week) 	<4,500, >=4,500 and <6,000, >=6,000
Prior ESA type	Epoetin, Epoetin beta pegol, Darbepoetin alfa
ERI (IU/kg/week/g/dL) 	By tertile
Period of Time on Dialysis (year)	< 5, >= 5 and < 10, >= 10
Baseline Iron Use 	Yes, No
Baseline Weight (kg)	< 55, >=55
Baseline BMI (kg/m  )	<20, >=20
History of Diabetes 	Yes, No

**NOTES:**

- BMI = Body Mass Index
  - See Section 15.6.1 for the subgroup derivations
- [1] Standardized dose on epoetin IV (IU/week) will be used.
- [2] Additional thresholds might be added in order to divide the population equally as appropriate.
- [3] See Section 15.6.2 for definition
- [4] Subjects who used ferric citrate (trade name: Riona) will also be included in Baseline Iron Use group. This category will be used only for iron analyses. See Section 15.6.6.
- [5] Past or current history of diabetes

## 5.5. Multiple Comparisons and Multiplicity

Adjustment for multiplicity will be applied to maintain an overall type I error rate of 2.5% (one-sided). After a preliminary assessment, the primary endpoint will be evaluated to demonstrate the non-inferiority at a one-sided significance level of 2.5%. Only when the primary endpoint achieves non-inferiority, statistical testing will progress to the principal secondary endpoint with a focus on superiority. Since the process will follow step-down manner, a multiplicity adjustment for one-sided significance level of 2.5% will not be needed according to a closed test procedure.

## 5.6. Other Considerations for Data Analyses and Data Handling Conventions

Other considerations for data analyses and data handling conventions are outlined in the appendices:

Section	Component
15.3	Appendix 3: Assessment Windows
15.4	Appendix 4: Study Phases and Treatment Emergent Adverse Events
15.5	Appendix 5: Data Display Standards & Handling Conventions
15.6	Appendix 6: Derived and Transformed Data
15.7	Appendix 7: Reporting Standards for Missing Data
15.8	Appendix 8: Values of Potential Clinical Importance

## 6. STUDY POPULATION ANALYSES

### 6.1. Overview of Planned Study Population Analyses

The study population analyses will be based on the specified population.

Study population analyses including analyses of subject's disposition, protocol deviations, population analyzed, demographic and baseline characteristics, prior and concomitant medications, and exposure and treatment compliance will be based on GSK Core Data Standards. Analyses of dialysis will also be included. Details of the planned displays are presented in [Appendix 10: List of Data Displays](#).

Endpoint / Parameter / Display Type	Population	Data Displays Generated		
		Table	Figure	Listing
Subject's Disposition				
Subject Status and Reason for Study Withdrawal	Randomized	Y		
Reasons for Study Withdrawal	Randomized			Y
Treatment Status and Reasons for Discontinuation of Study Treatment	Safety	Y		Y
Screening Status and Reasons for Screen Failure	All Screening	Y		Y
Subjects Enrolled by Country and Site ID	Enrolled	Y		
Subjects for Whom the Treatment Blind was Broken	Randomized			Y
Planned and Actual Treatments	Safety			Y
Protocol Deviations				
Important Protocol Deviations	Randomized	Y		Y
Subjects with Inclusion/Exclusion Criteria Deviations	Randomized	Y		Y
Populations Analyzed				
Study Populations	Randomized	Y		
Exclusion from the Per Protocol Population	mITT	Y		Y
Subjects Excluded from Any Population	Randomized			Y
Demographic and Baseline Characteristics				
Demographic Characteristics	ITT/Safety	Y		Y
Other Baseline Characteristics 	Safety			Y
Prior ESA	ITT/Safety	Y		Y
Age Ranges	Enrolled	Y		
Race and Racial Combinations	Safety	Y		Y 
Family History for CV Risk Factors	Safety	Y		Y
Substance Use (History of Tobacco Use, Alcohol Intake)	Safety	Y		Y
Dialysis				
Baseline Mode of Dialysis	Safety	Y		Y
Subjects with Change in Hemodialysis	Safety			Y
Baseline Mode of Vascular Access	Safety	Y		Y
Subjects with Vascular Therapeutic Procedures during the study period	Safety			Y
Subjects with Vascular Access Intervention / Revision	Safety			Y

Endpoint / Parameter / Display Type	Population	Data Displays Generated		
		Table	Figure	Listing
Medical Conditions and Concomitant Medications				
Current/Past Medical Conditions	Safety	Y		Y
Concomitant Medications 	Safety	Y		Y
Other Concomitant Medications (ESA, Iron, and Anti-Hypertensive Medications)	Safety	Y 		Y
Blood Products and Blood Supportive Care Products	Safety	Y		Y
Exposure and Treatment Compliance				
Exposure to Study Treatment	Safety	Y		Y
Treatment Compliance	Safety	Y		Y

**NOTES :**

- Y = Yes display generated.

[1] As a separate listing, include prior ESA type, standardized prior ESA dose, ERI, period of time on dialysis, iron use, and diabetes.

[2] Listing of race.

[3] Concomitant medications in pre-therapy, on-therapy, and post-therapy period will be summarized separately.

[4] On-therapy ESA, on-therapy iron, and on-therapy anti-hypertensive medications will be provided.

## 6.2. Planned Summary Display Details

Subjects who have multiple subject numbers (i.e. rescreened subjects) will be analyzed as unique subjects based on the latest screening results (see Section 15.6.1 and Section 15.6.2).

The definition of subgroup is described in Section 5.4.2.

- **Subject Disposition**

### Subject Status and Reason for Study Withdrawal

The number and percentage of subjects completing the study (see Appendix 7) or withdrawing early from the study will be summarized overall and by reason for withdrawal by treatment group and total. Reasons for withdrawal of subjects will be listed.

### Treatment Status and Reasons for Discontinuation of Study Treatment

The number and percentage of subjects completing the treatment or discontinuing the treatment during the study will be summarized overall and by reason (and subreason) by treatment group and total.

### Screening Status and Reasons for Screen Failure

The number and percentage of subjects who passed screening (i.e. enrolled) and who failed screening and were therefore not entered into the study will be summarized regardless of treatment group. Note that the reasons for rescreen subjects who initially failed but subsequently enrolled are not included in the display (see Section 15.6.2).

### Subjects Enrolled by Country and Site ID

The number and percentage of subjects by Country, Site ID and Investigator name will be summarized by treatment group and total.

- **Protocol Deviations**

#### Important Protocol Deviations

The number and percentage of subjects who had important protocol deviations defined in PDMP will be summarized by treatment group and total.

#### Subjects with Inclusion/Exclusion Criteria Deviations

The number and percentage of subjects, who were randomized into the trial, but deviated from the inclusion or exclusion criteria, will be summarized, further classifying inclusion/exclusion deviations by treatment group and total.

- **Population Analyzed**

#### Study Populations

The number and percentage of subjects in each analysis population (defined in Section 4) will be summarized by treatment group and total.

#### Exclusion from Per Protocol Population

The number of the exclusions from the PP population and the exclusion categories (See [Appendix 1](#)) will be summarized by treatment group and total.

- **Demographic and Baseline Characteristics**

#### Demographic Characteristics

The number and percentage of subjects or summary statistics will be provided by treatment group and total for the demographic and baseline characteristics: Sex, Age (years), Age Group (years), Ethnicity, Race detail, Height, Weight, and Body Mass Index. Age Group (years) will be categorized into 3 ('≤18', '19-64', '≥65'). Separate summaries for ITT and Safety population will be produced.

#### Prior ESA

For overall prior ESA, the weekly dose (standardized by IU/week), erythropoietin resistance index (ERI), and the number and percentage of subjects' dosing route (intravenous or subcutaneous) will be summarized by treatment group and total. These will be produced by type of prior ESA dose (epoetin, epoetin beta pegol, and darbepoetin

alfa). See Section 15.6.2 for standardized weekly dose and ERI. Separate summaries for ITT and Safety population will be produced.

#### Age Ranges

The number and percentage of subjects within each age range category will be provided by treatment group and total. Age range will be categorized into: 18-64 years, ≥65-84 years, ≥85 years.

#### Race and Racial Combinations

Summaries of race and racial combinations will be provided by treatment group and total.

#### Family History for CV Risk Factors

A summary of family (first degree relatives) history for CV risk factors will be provided by treatment group and total.

#### Substance Use (History of Tobacco Use, Alcohol Intake)

A summary of substance use will be provided by treatment group and total.

### • **Medical Conditions and Concomitant Medications**

#### Current/Past Medical Conditions

The number and percentage of subjects with current and past medical conditions recorded in eCRF will be provided by treatment group and total.

#### Concomitant Medications

The number and percentage of subjects reporting the use of each concomitant medication will be summarized by treatment group and total by anatomical therapeutic chemical (ATC) Level 1, and Ingredient. Summaries for pre-therapy, on-therapy, and post-therapy medication will be provided separately. See Section 15.4.1.2 for the study phases.

#### Other Concomitant Medications (On-Therapy ESA, Iron, and Anti-Hypertensive Medications)

The similar summary as above will be provided by treatment group and total focusing on on-therapy ESA, on-therapy iron medication, and on-therapy anti-hypertensive medications. See Section 15.4.1.2 for the study phases.

#### Blood Products and Blood Supportive Care Products (On-Therapy)

The number and percentage of subjects who use blood products and/or blood supportive care products will be provided by treatment group and total. The details for the use will also be summarized.

- **Dialysis**

Baseline Mode of Dialysis

The number and percentage of subjects with each baseline mode of dialysis (i.e. haemodialysis, haemofiltration, or haemodiafiltration) will be provided by treatment group and total. The period of time on dialysis (years) will be summarized using mean, standard deviation, median, minimum, and maximum.

Baseline Mode of Vascular Access

The number and percentage of subjects with each baseline mode of vascular access will be provided by treatment group and total. Previous vascular access will be summarized in the same manner.

- **Exposure and Treatment Compliance**

Exposure to Study Treatment

Full details of exposure definition are presented in Section [15.6.2](#).

Time on study treatment (days), subject daily dose (for daprodustat) or weekly dose (for darbepoetin alfa), and cumulative dose will be summarized using the number of subjects exposed, mean, standard deviation, median, minimum, and maximum. Time on study treatment will be categorized in different time periods (< 3 months, 3 months to 6 months, >6 months to 12 months, >12 months; 1 month = 30.4375 days) and the number and percentage of subjects exposed will be displayed for each category.

Treatment Compliance

Full details of treatment compliance definition are presented in Section [15.6.2](#).

The number and percentage of subjects within each category will be summarized by treatment and total for up to Week 4, Week 40 to 52, and overall. The categories will be classified into under compliant, compliant, over compliant. Note that this is a double-dummy study but a summary will be made for the active treatment and a listing will contain both active and placebo compliance.

## 7. EFFICACY ANALYSES

### 7.1. Primary Efficacy Analyses

#### 7.1.1. Endpoint / Variables

Endpoint / Parameter/ Display Type	Populatio n	Absolute						
		Stats Analysis			Summary		Individual	
		T	F	L	T	F	F	L
Mean Hgb Based on Observed Hgb During the Primary Efficacy Evaluation Period (i.e. Individual Mean of Hgb at Week 40, 44, 48, and 52)								
(Preliminary assessment) Observed Case mITT population	mITT				Y			
Model based Mean Hgb During the Primary Efficacy Evaluation Period								
(Primary) MMRM	ITT	Y	Y					
MMRM	mITT/PP	Y	Y					
MMRM By Subgroup	ITT	Y	Y 					
MMRM Evaluable Hgb	ITT	Y	Y					
Analysis of Covariance (ANCOVA)	mITT/PP	Y						
ANCOVA By Subgroup	mITT	Y	Y 					
Tipping Point Analysis	ITT/mITT/ PP	Y	Y					

#### NOTES :

- T = Table, F = Figure, L = Listing, Y = Yes display generated.
- Stats Analysis = Represents TFL related to any formal statistical analyses (i.e. modelling) conducted.
- Summary = Represents TFL related to any summaries (i.e. descriptive statistics) of the observed raw data.
- Individual = Represents FL related to any displays of individual subject observed raw data.

[1] Forest Plots

#### 7.1.2. Summary Measure

##### Mean Hgb based on observed Hgb during the primary efficacy evaluation period

The values will be summarized using mean, standard deviation, 95% CI, minimum, P25, median, P75, and maximum by treatment group.

##### Analysis of mean Hgb during the primary efficacy evaluation period

For ITT population, model-based mean Hgb will be estimated using a statistical model (Section 7.1.5). The point estimates of model-based mean Hgb for each treatment will be presented with standard error and 95% CI. For non-inferiority assessment at a one-sided significance level of 2.5%, the estimate of treatment difference, its 95% CI, and a non-inferiority p-value will be provided. Analysis will be repeated by the mITT and PP

populations in the same manner. The subgroup analysis based on the ITT population will also be produced using tables and a forest plot. (See Section 7.1.5 for the detail)

*Sensitivity/Supplementary analysis for mean Hgb during the primary efficacy evaluation period*

- Evaluable Hgb (Section 7.1.6.1 for the statistical analysis specifications)

Supplementary analysis using evaluable Hgb (See Section 15.6.3) based on the ITT population will be performed in the same manner as primary efficacy analysis using a mixed model for repeated measures.

- ANCOVA (Section 7.1.6.2 for the statistical analysis specifications)

Supplementary analysis using ANCOVA based on the mITT population will be summarized in the same manner as the primary efficacy analysis with the use of a mixed model for repeated measures. Analysis will be repeated for the PP population. The subgroup analysis based on the mITT population will also be produced using tables and a forest plot.

- Tipping Point Analysis (Section 7.1.6.3 for the statistical analysis specifications)

Tipping point sensitivity analysis based on the ITT population will be summarized using combined treatment differences, the associated 95% CIs and non-inferiority p-values by delta adjustments. Graphical display will be provided as a heatmap that represents non-inferiority p-values obtained from the test conducted for each delta adjustment. The horizontal and vertical axes indicate values of delta for daprodustat and darbepoetin alfa respectively. The color grids which highlight non-inferiority success or not will also be displayed.

### 7.1.3. Population of Interest

The primary efficacy analyses will be based on the ITT population, unless otherwise specified.

### 7.1.4. Strategy for Intercurrent (Post-Randomization) Events

Intercurrent events	Strategy
Study withdrawal	The following hypothetical scenario is considered; what would have happened if the event did not occur. The primary analyses using MMRM assume missing at random mechanism, that is the observations of missing depend on just observed values, not on unobserved values.

Intercurrent events	Strategy
Prohibited medications (except for commercial ESA medications)	Basically, the occurrence of the event is taken to be irrelevant. Subjects with long-term use of prohibited medications will be excluded from the PP population.
Blood transfusion and/or commercial ESA medication	In primary analyses, the occurrence of the event is taken to be irrelevant.
Intermittent missing	The following hypothetical scenario is considered to assess what would have happened if the event did not occur. The hypothesis is that an intermittent missing would occur at at-random manner, that is the observations of the missing depend on just observed values, not on unobserved values.

### 7.1.5. Statistical Analyses / Methods

Details of the planned displays are provided in [Appendix 10: List of Data Displays](#) and will be based on GSK data standards and statistical principles.

Unless otherwise specified, endpoints/variables defined in Section [7.1.1](#) will be summarized using descriptive statistics, graphically presented (where appropriate) and listed.

As a preliminary assessment, it will be confirmed whether the mean Hgb during the primary efficacy evaluation period in the daprodustat group would be in the target range (10.0-12.0 g/dL) at first. This confirmation will be established if the lower and upper limit of 95% CI for the mean Hgb based on observed Hgb during the primary efficacy evaluation period in daprodustat group would lie fully within the target range. After the stated confirmation, non-inferiority will be assessed at a one-sided significance level of 2.5%.

#### 7.1.5.1. Statistical Methodology Specification

Endpoint / Variables

 
Mean Hgb during the primary efficacy evaluation period (Week 40 to 52)
 

Model Specification

 
Analyses will be conducted by MMRM as follows:
 
 $\text{Hgb}_{ik} = \beta_0 + \beta_{\text{baseline}} * \text{Baseline}_i + \beta_j + \beta_k + \beta_{jk} + \beta_{\text{baseline}*j} * \text{Baseline}_i + \epsilon_{ik}$ 
Hgbi, week: Hgb measurement for subject i at visit k  <math>\beta_0</math>: Intercept

$\beta_{\text{baseline}}$ : baseline Hgb effect  
 Baselinei: Hgb measurement for subject i  
 $\beta_j$ : treatment effect (j= daprodustat, darbepoetin alfa)  
 $\beta_k$ : visit effect (k = Week 4, Week 8, ..., Week 52)  
 $\beta_{jk}$ : treatment-by-visit interaction  
 $\beta_{\text{baseline}*j}$ : baseline-by-visit interaction  
 $\epsilon_{ik}$ : random error for subject i at visit k  
 i: subject (i = 1, 2, ..., N)  
 N: number of subjects included in the analysis

- The model parameters will be estimated using Restricted Maximum Likelihood (method=REML) with the Newton-Raphson algorithm.
- The Kenward-Roger method for calculating the denominator degrees of freedom will be used.
- The variance-covariance structures for repeated measures within the individual subject will be unstructured (type=UN).
- LS means for treatment j at visit k will be calculated as follows.

$$\mu_{jk} = \beta_0 + \beta_{\text{baseline}} * \mu_{\text{baseline}} + \beta_j + \beta_k + \beta_{jk} + \beta_{\text{baseline}*k} * \mu_{\text{baseline}}$$

$\mu_{jk}$ : LS mean for treatment j at visit k  
 $\mu_{\text{baseline}}$ : mean for baseline Hgb

- Model based mean Hgb during the primary efficacy evaluation period for treatment j will be calculated as follows

$$\begin{aligned} \mu_j^{\text{evaluation}} &= (\mu_j^{\text{Week 40}} + \mu_j^{\text{Week 44}} + \mu_j^{\text{Week 48}} + \mu_j^{\text{Week 52}})/4 \\ &= \beta_0 + \beta_{\text{baseline}} * \mu_{\text{baseline}} + \beta_j + (\beta_{\text{Week 40}} + \beta_{\text{Week 44}} + \beta_{\text{Week 48}} + \beta_{\text{Week 52}})/4 + (\beta_j^{\text{Week 40}} + \beta_j^{\text{Week 44}} + \beta_j^{\text{Week 48}} + \beta_j^{\text{Week 52}})/4 + (\beta_{\text{baseline}*Week 40} + \beta_{\text{baseline}*Week 44} + \beta_{\text{baseline}*Week 48} + \beta_{\text{baseline}*Week 52}) * \mu_{\text{baseline}}/4 \end{aligned}$$

- The treatment difference for model based mean Hgb during the primary efficacy evaluation period will be calculated as follows

$$\begin{aligned} \mu_{\text{daprodustat}^{\text{evaluation}}} - \mu_{\text{darbepoetin alfa}^{\text{evaluation}}} &= \beta_{\text{daprodustat}} - \beta_{\text{darbepoetin alfa}} + (\beta_{\text{daprodustat}^{\text{Week 40}}} + \beta_{\text{daprodustat}^{\text{Week 44}}} + \beta_{\text{daprodustat}^{\text{Week 48}}} + \beta_{\text{daprodustat}^{\text{Week 52}}})/4 - (\beta_{\text{darbepoetin alfa}^{\text{Week 40}}} + \beta_{\text{darbepoetin alfa}^{\text{Week 44}}} + \beta_{\text{darbepoetin alfa}^{\text{Week 48}}} + \beta_{\text{darbepoetin alfa}^{\text{Week 52}}})/4 \end{aligned}$$

- P-value for non-inferiority test will be based on the following *t* test statistic (Mascha, 2011):

$$t = (\mu_{\text{daprodustat}^{\text{evaluation}}} - \mu_{\text{darbepoetin alfa}^{\text{evaluation}}} - \delta)/s$$

$\delta$ : non-inferiority margin (= -1.0 g/dL)

$s$ : standard error of treatment difference

The non-inferiority p-value is the probability of observing a larger value of *t* in a *t* distribution with degrees of freedom of the estimate of treatment difference based on the Kenward-Roger method.

### Model Checking & Diagnostics

- In case there is a problem with convergence of the unstructured (type=UN) variance-covariance, the following strategy will be examined.
  1. Use Fisher's scoring algorithm for the estimation method.

 
2. Set Heterogeneous Toeplitz (type=TOEPH) structure for variance-covariance structure.
 
3. In the event of that this model still fails to converge, alternative correlation structures may be considered such as type=CSH or CS.
 

Model Results Presentation

 
• The point estimates of LS mean Hgb during the primary efficacy evaluation period for each treatment will be presented with the associated standard errors and 95% CIs. For non-inferiority assessment at a one-sided significance level of 2.5%, the estimate of the treatment difference, standard error, its 95% CI, and a non-inferiority p-value will be provided.
 
• Non-inferiority will be established if the lower limit of the 95% CI for the treatment difference (daprodustat - darbepoetin alfa) of the mean Hgb during the primary efficacy evaluation period is greater than -1.0 g/dL (i.e., a p-value is smaller than 0.025).
 

Subgroup Analyses

 
• Treatment differences (daprodustat - darbepoetin alfa) of the mean Hgb during the primary efficacy evaluation period, standard errors, and the associated 95% CIs will be provided by each subgroup (See Section 5.4.2).
 
• The subgroup analyses will be based on the ITT population.
 
• The same statistical analysis method (using MMRM described as above) will be applied to estimate the mean Hgb during the primary efficacy evaluation period for each subgroup. If there is a problem with convergence for a certain subgroup, the result of the subgroup will not be displayed.
 
• Graphical summaries for the treatment differences of the mean Hgb during the primary efficacy evaluation period and the associated 95% CIs will be produced using a forest plot.
 

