9.2. Sample Size Considerations

9.2.1. Sample Size Assumptions

Assuming a non-inferiority margin of -1.0 g/dL, a treatment difference of 0.0 g/dL, and a standard deviation of 1.5 g/dL for mean Hgb during the primary efficacy evaluation period in HD subjects, two-sample t-test has at least 99% power at a one-sided significance level of 2.5% (i.e. two-sided significance level of 5%) with a sample size of 100 subjects per group. Assuming a dropout rate of approximately 25%, 135 subjects will be randomized to each group. Given the results from previous non-inferiority studies of similar drugs (darbepoetin alfa, epoetin beta pegol, and peginesatide), the non-inferiority margin of -1.0 g/dL is set. Since an increase of 1.0 g/dL indicates improvement in anemia according to the guidelines for renal anemia in Japan, the non-inferiority margin of -1.0 g/dL may be the clinically acceptable largest difference in renal anemia.

While the present study is designed to ensure long-term safety data from 100 HD subjects, and the primary hypothesis test has at least 99% power to estimate the efficacy very precisely, non-inferiority can be statistically demonstrated with a minimum between-group difference of -0.582 g/dL.

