## 2.4. Statistical Hypotheses / Statistical Analyses

The primary objective of the study is to demonstrate the non-inferiority of daprodustat to darbepoetin alfa based on mean Hgb during the primary efficacy evaluation period (Weeks 40 to 52) in HD subjects.

As a preliminary assessment, it will be confirmed whether the mean Hgb during the primary efficacy evaluation period in daprodustat group would be in target range (10.0-12.0 g/dL) at first. And then the following non-inferiority statistical hypotheses are to be tested at a one-sided significance level of 2.5%:

- $H_0$ : Treatment difference in mean Hgb during the primary efficacy evaluation period, between treatment arms (daprodustat – darbepoetin alfa), is  $-1.0$  g/dL or less.
- $H_1$ : Treatment difference in mean Hgb during the primary efficacy evaluation period, between treatment arms (daprodustat – darbepoetin alfa), is greater than  $-1.0$  g/dL.

Only when the primary endpoint achieves non-inferiority, statistical testing will progress to the principal secondary endpoint with a focus on superiority according to the step-down procedure. More specifically, the superiority of daprodustat to darbepoetin alfa in terms of target Hgb control in HD subjects is to be demonstrated at a one-sided significance level of 2.5% by testing the following statistical hypotheses:

- $H_0$ : The proportion of subjects whose mean Hgb during the primary efficacy evaluation period is within the target range (10.0-12.0 g/dL) is equal between the treatment groups.

- H1: The proportion of subjects whose mean Hgb during the primary efficacy evaluation period is within the target range (10.0-12.0 g/dL) is different between the treatment groups.

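### The last MMRM covariance fallback (CSH or CS) keeps the model-based standard error, so the primary confidence interval would be too narrow if that step is reached and Hgb correlation decays over time

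*SAP*

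**What the plan says.** SAP 2.4 sets the level: "And then the following non-inferiority statistical hypotheses are to be tested at a one-sided significance level of 2.5"%. SAP 7.1.5.1 specifies a REML model over 13 visits (every 4 weeks, Week 4 to Week 52) with treatment, visit, baseline Hgb and the two by-visit interactions. The covariance is unstructured, and "The Kenward-Roger method for calculating the denominator degrees of freedom will be used". The estimate is the difference between arms in the equal-weight average of the LS means at Weeks 40, 44, 48 and 52. The t statistic divides by the standard error of that difference, with no statement of how it is estimated beyond the model.

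The Model Checking & Diagnostics part of the same section covers convergence failure: first Fisher scoring, then TOEPH. If that also fails, "alternative correlation structures may be considered such as type=CSH or CS". No order between CSH and CS is given, and no empirical standard error is mentioned at any step.

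**The concern.** A fallback is written down in advance so that the confirmatory test keeps its level when the first model cannot be fitted. CS and CSH give every pair of visits the same correlation, whether 4 or 48 weeks apart. If Hgb values close in time are more alike than values far apart, the fitted correlation is a compromise that is too low for four adjacent visits. The variance of their mean is then understated. Kenward-Roger allows for the estimation of covariance parameters within the assumed structure; it does not correct a wrong structure.

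At stake are the primary confidence interval and non-inferiority p-value, and through SAP 5.5 the gate to the superiority test. The choice within step 3 would also be made late: SAP 3.2 places release of the randomization codes before the final analyses.

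**Working it through.** **Inputs from the documents.** Protocol 9.2.1: "Assuming a non-inferiority margin of -1.0 g/dL", "a treatment difference of 0.0 g/dL", "a standard deviation of 1.5 g/dL for mean Hgb during the primary efficacy evaluation period", "with a sample size of 100 subjects per group", and about 25% dropout. SAP 7.1.5.1: 13 visits, contrast over the last four. **Not in the documents:** within-subject correlations and visit-by-visit variances. Everything in steps 2 to 4 rests on assumed values for these.

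**1. The plan's own figure.** SE = 1.5 x sqrt(2/100) = 0.2121. With 198 df the critical value is 1.972 and the noncentrality is 1/0.2121 = 4.71, giving power 99.68% (Protocol Table 13: 99.7%). The smallest observed difference that still passes is -1 + 1.972 x 0.2121 = -0.582 g/dL, as stated in 9.2.1. This calculation treats the period mean as one value per subject, so it says nothing about correlation between visits.

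**2. Formula.** With variance v and common covariance c, the mean of four visits has variance (v + 3c)/4. With complete data and a large sample, a CS fit sets v to the average of the 13 visit variances and c to the average of the 78 covariances. The SE ratio is q = sqrt(model variance / true variance), and the one-sided error at the margin is Phi(-1.96 q).

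**3. Equal variances, AR(1) with 4-week correlation 0.7.**
- Average correlation among the last four visits: (3 x 0.7 + 2 x 0.49 + 0.343)/6 = 0.5705. True variance: (1 + 3 x 0.5705)/4 = 0.678.
- Average over all 78 pairs: sum over k = 1 to 12 of (13 - k) x 0.7^k, divided by 78, = 0.290. Model variance: (1 + 3 x 0.290)/4 = 0.468.
- q = sqrt(0.468/0.678) = 0.83, so the interval is 17% too narrow, with error Phi(-1.63) = 5.2%. A Monte Carlo run (20,000 trials, 101 per arm, complete data) gave q = 0.827 and 4.9%.

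The same method over other assumptions, taking CS and CSH together unless stated:

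| Assumed truth | CI too narrow by | One-sided error |
|---|---|---|
| AR(1) 0.4-0.9, no dropout | 6-18% | 3.3-5.3% |
| AR(1) 0.4-0.9, 25% dropout | 11-21% | 4.1-6.0% |
| AR(1) 0.95 | 3-9% | 2.9-3.7% |
| Decay to a floor of 0.2-0.5 | 5-16% | 3.1-5.0% |
| SD rising 20-50%, plain CS | 16-31% | 5.0-8.9% |
| SD falling, plain CS | 2-14% | 2.7-4.6% |
| CS true | 0% | 2.5% |

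CSH did not exceed 21% and 6.0% in any case, because it carries visit-specific variances.

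**4. Why rising variance matters here.** The model adjusts for baseline at each visit. If correlation decays, baseline explains early visits well and late visits poorly, so residual variance grows. Take AR(1) 0.9 including baseline. The residual covariance of visits j and k is 0.9^|j-k| - 0.9^(j+k), so the residual variance is 1 - 0.81 = 0.19 at Week 4 and 1 - 0.9^26 = 0.935 at Week 52.
- Averages over 13 visits are v = 0.693 and c = 0.376, so the CS model variance is (0.693 + 3 x 0.376)/4 = 0.455.
- True variance over the last four: 0.881 before adjustment, less the square of the mean of 0.9^10 to 0.9^13 (0.300^2 = 0.090), which is 0.791.
- q = sqrt(0.455/0.791) = 0.76: 24% too narrow, error Phi(-1.49) = 6.8%.

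Across assumed patterns, conditioning on baseline gives 14-31% and 4.6-8.9% for plain CS.

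**5. Effect on the decision.** On the planning inputs the passing threshold is -1 + 1.972 x q x 0.2121. For an interval 10%, 20%, 25% or 30% too narrow this is -0.624, -0.665, -0.686 or -0.707 g/dL, against -0.582.

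**The case against.** Four points count against giving this much weight, and all stand in part.

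- **The route is remote.** Step 3 needs the unstructured fit, Fisher scoring and TOEPH all to fail. The unstructured matrix has 13 x 14/2 = 91 parameters for about 270 subjects with up to 13 visits each. TOEPH has 13 + 12 = 25 and already lets correlation vary with lag. Nothing in the documents suggests that failure is likely.
- **The SAP does not commit to CSH or CS.** They are examples, so ARH(1) would already be permissible. That is true, but it leaves the choice open rather than safe.
- **The consequence is bounded.** The error rate applies at a true difference of -1.0 g/dL, while planning assumes 0.0. Only observed differences between about -0.58 and -0.71 g/dL would change outcome, even at the top of the range.
- **ANCOVA on each subject's mean is planned** (SAP 7.1.6.2) and does not depend on the MMRM covariance. It is supplementary and run in the mITT and PP populations, so it does not protect the primary ITT result.

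A reader might also extend the point to the iron and QoL models, since SAP 7.4.5.1 repeats the same ladder and 9.5.1 refers to that model. The argument does not carry over. Those models report the treatment difference at single visits, whose standard error does not rest on the correlation within a block of adjacent visits. They carry no confirmatory test.

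**Conclusion.** The gap is real but conditional. If step 3 is reached with CS or CSH, and Hgb correlation falls with time between visits, the primary interval is too narrow: roughly 5-20%, with one-sided error about 3-6%. For plain CS with residual variance rising over time the shortfall reaches about 25-30%, with error about 7-8.5%. It is nil if CS is true, and small if correlation is very high without rising residual variance.

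A reader might infer that the fallback inflates the error by a fixed amount, or that the planned primary analysis fails to hold 2.5%. The documents support neither. They give no correlations from which to fix a figure, and the unstructured model with Kenward-Roger is not affected. With the -1.0 g/dL margin and 99.7% planned power, the non-inferiority decision would probably survive; the reported interval and p-value would still be wrong.

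**What to change.** In SAP 7.1.5.1 only, add: *If a covariance structure other than unstructured is used, standard errors, confidence intervals and p-values will come from the empirical (sandwich) estimator with between-within degrees of freedom.* In step 3, replace the open-ended CSH/CS wording by a fixed order that starts with a structure whose correlation falls with time, such as ARH(1).

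Both parts are needed. The sandwich estimator corrects the standard error; a realistic structure also limits any bias in the estimate when dropout depends on observed Hgb. In a simulation of CS fits with 135 per arm, 13 visits and 24% dropout depending on the last Hgb, the sandwich standard error brought the one-sided error to 1.8-3.0%.

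The cost is a short wording change before unblinding. Kenward-Roger is given up in the fallback case only, a small loss with about 270 subjects, and SAP 7.1.6.3 already accepts between-within degrees of freedom for the imputed datasets. Nothing changes if the unstructured model converges.
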